1.0 PROTOCOL SYNOPSIS

Study Title:	Clinical Evaluation of Low Power Radiofrequency Energy Applied to the Posterior Nasal Nerve Area for Symptomatic Relief of Chronic Rhinitis
Study Device:	Aerin Medical InSeca ARC Stylus
Device Description:	The InSeca ARC Stylus is a disposable handheld device capable of delivering bipolar radiofrequency energy to tissue.
Indication:	The InSeca ARC Stylus is indicated for use in otorhinolaryngology (ENT) surgery for the coagulation of soft tissue in the nasal airway, to treat nasal airway obstruction by shrinking submucosal tissue.
Study Objective:	The primary objective of this study is to collect clinical data on the use of the InSeca ARC System to treat tissue in the posterior nasal nerve area to improve symptoms in adults diagnosed with chronic rhinitis.
Study Design:	Prospective, multicenter, nonrandomized, nonsignificant Risk (NSR) study.
Subject Population:	Male and female subjects who present with symptoms associated with chronic rhinitis and meet the protocol eligibility criteria.
Study Procedure:	Subjects will have BOTH nostrils treated in the portion of the nasal cavity mucosa overlying the region of the posterior nasal nerve (the posterior middle meatus and posterior inferior meatus). Follow-up visits will be scheduled and calculated from the treatment date. No repeat ("touch-up") procedures will be permitted during the 52-week follow-up period.
Study Endpoints:	Primary Efficacy Endpoint : Mean change in the rTNSS score from baseline to 12 weeks post study procedure. For study success, the mean change must show an improvement (decrease) exceeding 1 point.
	Primary Safety Endpoint : Safety will be assessed by characterizing the type and frequency of adverse events reported at or following the study procedure, and throughout the follow-up period.
Additional Evaluations:	Responder Rate : A responder is defined as a treated subject who experiences at least a 1 point improvement (decrease) in the rTNSS score at 12 weeks compared to baseline score. An overall responder rate of at least 55% is expected for the study.
	rTNSS Scores Over Time : rTNSS scores and change from baseline will be summarized at baseline and each follow-up evaluation.
	rTNSS Individual Nasal Symptom Scores : The scores of each survey question will be summarized at baseline and each follow-up evaluation.

Subject Satisfaction Survey: The responses will be summarized for each follow-up evaluation at which the survey is administered. Nasal Status Assessment: Each component of the assessment will be summarized at baseline and each follow-up evaluation. VAS Pain Scores: VAS pain scores will be summarized at th immediate post-treatment evaluation and at the 2-, 4-, and 12-wee follow-up evaluations: Medications: Medication information will be summarized and reviewer for significant trends. Study Size: 50 subjects who meet the inclusion/exclusion criteria and enroll in the study Number of Study Sites: Up to 10 study sites Anticipated Study Duration: Enrollment completion – Q1 2019; Follow-Up completion – Q1 2020 Study Visits: Screening/Baseline, Study Procedure, 2 weeks, 4 weeks, 12 weeks, 2 weeks, 52 weeks Study Eligibility Criteria: Inclusion Criteria: Eligible subject will meet all the following: 1. Age 22 to 75 years (inclusively) 2. Willing and able to comply with the subject-specific requirement outlined in the study protocol 4. Seeking treatment for chronic rhinitis symptoms of at least 6 month duration and willing to undergo an office-based procedure 5. Moderate to severe symptoms of rhinorrhea (rTNSS rating of 2, or for rhinorrhea) 6. Mild to severe symptoms of nasal congestion (rTNSS rating of 1, i or 3 for congestion)		QOL Questionnaire : The responses for each of the 9 questions will be summarized at baseline and each follow-up evaluation at which the survey is administered.					
Nasal Status Assessment: Each component of the assessment will b summarized at baseline and each follow-up evaluation. VAS Pain Scores: VAS pain scores will be summarized at th immediate post-treatment evaluation and at the 2-, 4-, and 12-wee follow-up evaluations. Medications: Medications: Medications: Study Size: S0 subjects who meet the inclusion/exclusion criteria and enroll in the study Number of Study Sites: Up to 10 study sites Anticipated Study Duration: Enrollment completion – Q1 2019; Follow-Up completion – Q1 2020 Study Visits: Screening/Baseline, Study Procedure, 2 weeks, 4 weeks, 12 weeks, 2 weeks, 52 weeks Study Eligibility Criteria: Inclusion Criteria: Eligible subject will meet all the following: 1. Age 22 to 75 years (inclusively) 2. Willing and able to provide informed consent 3. Willing and able to comply with the subject-specific requirement outlined in the study protocol 4. Seeking treatment for chronic rhinitis symptoms of at least 6 month duration and willing to undergo an office-based procedure 5. Moderate to severe symptoms of nasal congestion (rTNSS rating of 2 or for rhinorrhea) 6. Mild to severe symptoms of nasal congestion (rTNSS rating of 1, i or 3 for congestion) 7. rTNSS score of ≥ 6 8. Dissatisfaction with medical management, defined as usage on in		Subject Satisfaction Survey : The responses will be summarized for each follow-up evaluation at which the survey is administered.					
VAS Pain Scores: VAS pain scores will be summarized at th immediate post-treatment evaluation and at the 2-, 4-, and 12-wee follow-up evaluations. Medications: Medication information will be summarized and reviewee for significant trends. Study Size: Study Size: 50 subjects who meet the inclusion/exclusion criteria and enroll in the study Number of Study Sites: Up to 10 study sites Anticipated Study Duration: Enrollment completion – Q1 2019; Follow-Up completion – Q1 2020 Study Visits: Screening/Baseline, Study Procedure, 2 weeks, 4 weeks, 12 weeks, 2 weeks, 52 weeks Study Eligibility Criteria: Inclusion Criteria: Eligible subject will meet all the following: 1. Age 22 to 75 years (inclusively) 2. Willing and able to provide informed consent 3. Willing and able to comply with the subject-specific requirement outlined in the study protocol 4. Seeking treatment for chronic rhinitis symptoms of at least 6 month duration and willing to undergo an office-based procedure 5. Moderate to severe symptoms of rhinorrhea (rTNSS rating of 2 or for rhinorrhea) 6. Mild to severe symptoms of nasal congestion (rTNSS rating of 1, or 3 for congestion) 7. rTNSS score of ≥ 6 8. Dissatisfaction with medical management		Nasal Status Assessment : Each component of the assessment will be summarized at baseline and each follow-up evaluation.					
Medications:Medication information will be summarized and reviewed for significant trends.Study Size:50 subjects who meet the inclusion/exclusion criteria and enroll in the studyNumber of Study Sites:Up to 10 study sitesAnticipated Study Duration:Enrollment completion – Q1 2019; Follow-Up completion – Q1 2020Study Visits:Screening/Baseline, Study Procedure, 2 weeks, 4 weeks, 12 weeks, 2 weeks, 52 weeksStudy Eligibility Criteria:Inclusion Criteria: Eligible subject will meet all the following: 1. Age 22 to 75 years (inclusively) 2. Willing and able to provide informed consent 		VAS Pain Scores : VAS pain scores will be summarized at the immediate post-treatment evaluation and at the 2-, 4-, and 12-week follow-up evaluations.					
Study Size: 50 subjects who meet the inclusion/exclusion criteria and enroll in the study Number of Study Sites: Up to 10 study sites Anticipated Study Duration: Enrollment completion – Ql 2019; Follow-Up completion – Ql 2020 Study Visits: Screening/Baseline, Study Procedure, 2 weeks, 4 weeks, 12 weeks, 2 weeks, 52 weeks Study Eligibility Criteria: Inclusion Criteria: Eligible subject will meet all the following: Age 22 to 75 years (inclusively) Willing and able to provide informed consent Willing and able to comply with the subject-specific requirement outlined in the study protocol Seeking treatment for chronic rhinitis symptoms of at least 6 month duration and willing to undergo an office-based procedure Moderate to severe symptoms of rhinorrhea (rTNSS rating of 2 or for rhinorrhea) Mild to severe symptoms of nasal congestion (rTNSS rating of 1, 5 or 3 for congestion) rTNSS score of ≥ 6 Dissatisfaction with medical management, defined as usage on intranasal steroids for a minimum of 4 weeks without adequat symptom relief, as judged by the subject 		Medications : Medication information will be summarized and reviewed for significant trends.					
Number of Study Sites:Up to 10 study sitesAnticipated Study Duration:Enrollment completion – Q1 2019; Follow-Up completion – Q1 2020Study Visits:Screening/Baseline, Study Procedure, 2 weeks, 4 weeks, 12 weeks, 2 weeks, 52 weeksStudy Eligibility Criteria:Inclusion Criteria: Eligible subject will meet all the following:1.Age 22 to 75 years (inclusively)2.Willing and able to provide informed consent3.Willing and able to comply with the subject-specific requirement outlined in the study protocol4.Seeking treatment for chronic rhinitis symptoms of at least 6 month 	Study Size:	50 subjects who meet the inclusion/exclusion criteria and enroll in the study					
Anticipated Study Duration: Enrollment completion – Q1 2019; Follow-Up completion – Q1 2020 Study Visits: Screening/Baseline, Study Procedure, 2 weeks, 4 weeks, 12 weeks, 2 weeks Study Eligibility Criteria: Inclusion Criteria: Eligible subject will meet all the following: 1. Age 22 to 75 years (inclusively) 2. Willing and able to provide informed consent 3. Willing and able to comply with the subject-specific requirement outlined in the study protocol 4. Seeking treatment for chronic rhinitis symptoms of at least 6 month duration and willing to undergo an office-based procedure 5. Moderate to severe symptoms of rhinorrhea (rTNSS rating of 2 or for rhinorrhea) 6. Mild to severe symptoms of nasal congestion (rTNSS rating of 1, i or 3 for congestion) 7. rTNSS score of ≥ 6 8. Dissatisfaction with medical management, defined as usage on intranasal steroids for a minimum of 4 weeks without adequat symptom relief, as judged by the subject	Number of Study Sites:	Up to 10 study sites					
Study Visits: Screening/Baseline, Study Procedure, 2 weeks, 4 weeks, 12 weeks, 2 weeks Study Eligibility Criteria: Inclusion Criteria: Eligible subject will meet all the following: 1. Age 22 to 75 years (inclusively) 2. Willing and able to provide informed consent 3. Willing and able to comply with the subject-specific requirement outlined in the study protocol 4. Seeking treatment for chronic rhinitis symptoms of at least 6 month duration and willing to undergo an office-based procedure 5. Moderate to severe symptoms of rhinorrhea (rTNSS rating of 2 or for rhinorrhea) 6. Mild to severe symptoms of nasal congestion (rTNSS rating of 1, 5 or 3 for congestion) 7. rTNSS score of ≥ 6 8. Dissatisfaction with medical management, defined as usage or intranasal steroids for a minimum of 4 weeks without adequat symptom relief, as judged by the subject	Anticipated Study Duration:	Enrollment completion – Q1 2019; Follow-Up completion – Q1 2020					
 Study Eligibility Criteria: Inclusion Criteria: Eligible subject will meet all the following: Age 22 to 75 years (inclusively) Willing and able to provide informed consent Willing and able to comply with the subject-specific requirement outlined in the study protocol Seeking treatment for chronic rhinitis symptoms of at least 6 month duration and willing to undergo an office-based procedure Moderate to severe symptoms of rhinorrhea (rTNSS rating of 2 or for rhinorrhea) Mild to severe symptoms of nasal congestion (rTNSS rating of 1, 5 or 3 for congestion) rTNSS score of ≥ 6 Dissatisfaction with medical management, defined as usage or intranasal steroids for a minimum of 4 weeks without adequat symptom relief, as judged by the subject 	Study Visits:	Screening/Baseline, Study Procedure, 2 weeks, 4 weeks, 12 weeks, 26 weeks, 52 weeks					
 Age 22 to 75 years (inclusively) Willing and able to provide informed consent Willing and able to comply with the subject-specific requirement outlined in the study protocol Seeking treatment for chronic rhinitis symptoms of at least 6 month duration and willing to undergo an office-based procedure Moderate to severe symptoms of rhinorrhea (rTNSS rating of 2 or for rhinorrhea) Mild to severe symptoms of nasal congestion (rTNSS rating of 1, 1 or 3 for congestion) rTNSS score of ≥ 6 Dissatisfaction with medical management, defined as usage or intranasal steroids for a minimum of 4 weeks without adequat symptom relief, as judged by the subject 	Study Eligibility Criteria:	Inclusion Criteria: Eligible subject will meet all the following:					
 Willing and able to provide informed consent Willing and able to comply with the subject-specific requirement outlined in the study protocol Seeking treatment for chronic rhinitis symptoms of at least 6 month duration and willing to undergo an office-based procedure Moderate to severe symptoms of rhinorrhea (rTNSS rating of 2 or for rhinorrhea) Mild to severe symptoms of nasal congestion (rTNSS rating of 1, 2 or 3 for congestion) rTNSS score of ≥ 6 Dissatisfaction with medical management, defined as usage or intranasal steroids for a minimum of 4 weeks without adequat symptom relief, as judged by the subject 		1. Age 22 to 75 years (inclusively)					
 Willing and able to comply with the subject-specific requirement outlined in the study protocol Seeking treatment for chronic rhinitis symptoms of at least 6 month duration and willing to undergo an office-based procedure Moderate to severe symptoms of rhinorrhea (rTNSS rating of 2 or for rhinorrhea) Mild to severe symptoms of nasal congestion (rTNSS rating of 1, 1 or 3 for congestion) rTNSS score of ≥ 6 Dissatisfaction with medical management, defined as usage or intranasal steroids for a minimum of 4 weeks without adequat symptom relief, as judged by the subject 		2. Willing and able to provide informed consent					
 4. Seeking treatment for chronic rhinitis symptoms of at least 6 month duration and willing to undergo an office-based procedure 5. Moderate to severe symptoms of rhinorrhea (rTNSS rating of 2 or for rhinorrhea) 6. Mild to severe symptoms of nasal congestion (rTNSS rating of 1, 2 or 3 for congestion) 7. rTNSS score of ≥ 6 8. Dissatisfaction with medical management, defined as usage or intranasal steroids for a minimum of 4 weeks without adequat symptom relief, as judged by the subject 		3. Willing and able to comply with the subject-specific requirements outlined in the study protocol					
 5. Moderate to severe symptoms of rhinorrhea (rTNSS rating of 2 or for rhinorrhea) 6. Mild to severe symptoms of nasal congestion (rTNSS rating of 1, 2 or 3 for congestion) 7. rTNSS score of ≥ 6 8. Dissatisfaction with medical management, defined as usage or intranasal steroids for a minimum of 4 weeks without adequat symptom relief, as judged by the subject 		4. Seeking treatment for chronic rhinitis symptoms of at least 6 months duration and willing to undergo an office-based procedure					
 6. Mild to severe symptoms of nasal congestion (rTNSS rating of 1, 2 or 3 for congestion) 7. rTNSS score of ≥ 6 8. Dissatisfaction with medical management, defined as usage or intranasal steroids for a minimum of 4 weeks without adequat symptom relief, as judged by the subject 		5. Moderate to severe symptoms of rhinorrhea (rTNSS rating of 2 or 3 for rhinorrhea)					
 7. rTNSS score of ≥ 6 8. Dissatisfaction with medical management, defined as usage or intranasal steroids for a minimum of 4 weeks without adequat symptom relief, as judged by the subject 		6. Mild to severe symptoms of nasal congestion (rTNSS rating of 1, 2 or 3 for congestion)					
 Dissatisfaction with medical management, defined as usage or intranasal steroids for a minimum of 4 weeks without adequat symptom relief, as judged by the subject 		7. rTNSS score of ≥ 6					
		8. Dissatisfaction with medical management, defined as usage of intranasal steroids for a minimum of 4 weeks without adequate symptom relief, as judged by the subject					

Exclusion Criteria:

Subject will not be enrolled if they meet any of the following:

- 1. Anatomic obstructions that in the investigator's opinion limit access to the posterior nose
- 2. Altered anatomy of the posterior nose as a result of prior sinus or nasal surgery or injury
- 3. Active nasal or sinus infection
- 4. Moderate to severe ocular allergic symptoms (such as eye tearing [epiphora], itching [pruritus], or redness [erythema])
- 5. History of significant dry eye
- 6. History of any of the following: nose bleeds in the past 3 months, rhinitis medicamentosa, head or neck irradiation
- 7. Known or suspected allergies or contraindications to the anesthetic agents and/or antibiotic medications to be used during the study procedure session
- 8. Known or suspected to be pregnant, or is lactating
- 9. Participating in another clinical research study
- 10. Other medical conditions which in the opinion of the investigator would predispose the subject to poor wound healing, increased surgical risk, or poor compliance with the requirements of the study

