13.2 Study Hypothesis

The primary endpoint of the study is change in mean rTNSS score from baseline to the 12-week evaluation. Improvement in the rTNSS score is represented by a decrease from baseline in the 12-point score. The minimum clinically important difference (MCID) for change in mean TNSS score derived from anchor-based methodologies has been shown to be 0.23 - 0.28 units and by distribution-based methodology the MCID was 0.59 units.²⁰ A less rigorous expert panel-based estimate of the MCID was 30% of the maximum score of 12, which is 3.6 units.²¹ The evidence-based thresholds for MCID have been recommended to supersede the panel-based method.^{22,23} An MCID of 1 unit, or 2 to 4 times the more rigorously derived MCIDs, was set for this study.

The hypothesis is that the improvement (decrease) in rTNSS mean score, measured as change from baseline at 12 weeks (12 weeks - baseline), exceeds the MCID (1 unit).

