13.3 Sample Size Estimate

Sample size estimation was based on a paired t-test for change from baseline at 12 weeks using the following assumptions:

- Significance level $\alpha = 0.05$ (one-sided)
- Power = 90%
- MCID = 1-point decrease in mean change score = the minimum clinically important difference
- μ_d = -2-point decrease in mean change score = the minimum expected observed difference
- SD = 2 = the expected standard deviation of the observed mean difference
- 10% dropout and nonevaluable.

The minimum number of subjects to achieve 90% power is 36 (G-Power, paired t-test).

The overall planned study sample size is 50 subjects. Fifty subjects allows for the possibility that findings from the review of the phase-1 initial subjects, with respect to the planned protocol treatment parameters, leads to significant protocol modifications to the procedure parameters for the remainder of the subjects. Significant modifications would exclude the initial subjects from the primary endpoint analysis, but a sufficient number of subjects would remain for analysis of the primary study hypothesis.

The sample size estimate will be re-evaluated after the standard deviation of the mean change for the phase-1 initial subjects has been obtained. If the observed standard deviation is larger than the assumed standard deviation, the sample size may be recalculated to assure adequate study size to evaluate the study hypothesis. This evaluation will not be an efficacy evaluation and will not be used to halt the study based on an early determination of success or to decrease the planned sample size.

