13.5 Missing Data

All efforts will be made to collect all data points in this study. The study hypothesis will be tested using all available data for the subjects in the evaluable patient population. If the primary endpoint is not available for all such subjects, then sensitivity analysis will be performed to assess the potential effect of missing data on the study conclusion. The sensitivity analysis will be performed by imputing all missing data points for the primary endpoint as no (0) improvement. If the study conclusion is upheld using this type of worst-case scenario, no other analysis will be performed. However, if the conclusion using imputed data is different, a multiple imputation approach may be used to gain further insight to the results.

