13.9 Primary Efficacy Endpoint Analysis

The mean change in the rTNSS score from baseline to 12 weeks will be tested using a paired t-test for a significant decrease greater than the MCID under the one-sided null (H_0) and alternative (H_A) hypotheses:

H₀:
$$\mu_d \ge -1$$

 $H_A: \mu_d < -1$

where μ_d = the mean change of the paired differences of the 12-week score - the baseline score.

A p-value for the test statistic ≤ 0.05 will indicate that the mean decrease is statistically significantly greater than 1 point. The upper limit of the one-sided 95% confidence interval on the mean decrease will also be calculated.

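### Does the synopsis leave study success resting on the observed mean change rather than on the Section 13.9 test?

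*Combined protocol and SAP*

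**What the plan says.** The synopsis (Section 1.0), under the primary efficacy endpoint, states: "For study success, the mean change must show an improvement (decrease) exceeding 1 point". No other section attaches a condition to study success.

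Section 13.2 puts the same margin as a hypothesis: "The hypothesis is that the improvement (decrease) in rTNSS mean score, measured as change from baseline at 12 weeks", exceeds the 1-unit MCID. Section 13.3 sizes the study for a paired t-test at a one-sided 0.05 level and lists as an input "MCID = 1-point decrease in mean change score = the minimum clinically important difference". Section 13.9 sets the null as a mean change (12-week minus baseline) of -1 or higher and the alternative as below -1, and adds: "A p-value for the test statistic ≤ 0.05 will indicate that the mean decrease is statistically significantly greater than 1 point". It then says: "The upper limit of the one-sided 95% confidence interval on the mean decrease will also be calculated".

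Section 13.5 says that the study hypothesis will be tested on the available data of the evaluable population. It then calls for a sensitivity analysis that sets missing values to no improvement, and continues: "If the study conclusion is upheld using this type of worst-case scenario, no other analysis will be performed".

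**The concern.** The one sentence that mentions a condition for success gives a margin and no inferential rule. The section with the inferential rule does not say that passing it is success. A literal reader could take the synopsis as a rule on the observed mean. That rule would declare success half the time when the true decrease is exactly 1 point, against 5% for the test. In a single-arm study with a self-rated score, the margin test is the only formal hurdle, so this would matter.

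Two related points looked open. Section 13.5 turns on whether the study conclusion is upheld, without repeating what counts as the conclusion. And the confidence-limit sentence in Section 13.9 asks for an upper limit on the mean decrease, although the sentence before it treats the decrease as a positive quantity, for which the lower limit would match the test.

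**Working it through.** **Inputs (Section 13.3).** One-sided alpha 0.05; power 90%; null decrease 1; expected decrease 2; SD of the change 2; 10% dropout or nonevaluable; stated minimum 36; planned total 50.

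**1. Reproduce the plan's figure.** For a one-sided paired t-test the distance from the null is 2 - 1 = 1. The noncentral t gives n = 36 with power 0.9026, as stated. A two-sided t-test would need 44, and a null of zero (distance 2, one-sided) would need 11. The total also fits: 50 - 10 first-phase subjects = 40, and 40 × 0.90 = 36.

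**2. Size the study on the literal rule instead.** The chance that the observed decrease exceeds 1 when the true decrease is 2 is Φ(1 / (2/√n)) = Φ(√n / 2). For 90% this needs √n / 2 ≥ 1.2816, so n ≥ (2 × 1.2816)² = 6.57, that is 7 subjects. The plan's 36 was not built on such a rule.

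**3. How far apart the readings would be.** The test passes when the observed decrease is at least 1 + t(0.95, n-1) × 2/√n (observed SD taken as 2):

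| n | Observed decrease needed | Test power at true decrease 2 |
|---|---|---|
| 36 | 1.563 | 90.3% |
| 40 | 1.533 | 92.8% |
| 45 | 1.501 | 95.1% |
| 50 | 1.474 | 96.7% |

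Pass rates at n = 45:

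| True decrease | Literal rule | Section 13.9 test |
|---|---|---|
| 1.0 | 50% | 5% |
| 1.2 | 75% | 16% |
| 1.5 | 95% | 50% |
| 2.0 | 99.96% | 95.1% |

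Example: observed decrease 1.3, n = 45. SE = 2/√45 = 0.298; t = 0.3/0.298 = 1.006; p = 0.160. The literal words are met and the test fails.

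**4. Section 13.5.** Take 45 observed (mean decrease 1.60, SD 2) and 5 missing set to 0. Before imputation: t = 0.60/0.298 = 2.01, p = 0.025. After: mean = 45 × 1.60/50 = 1.44; SD = √[(44 × 4 + 45 × 1.60² - 50 × 1.44²)/49] = 1.956; t = 0.44/(1.956/√50) = 1.590; p = 0.059. The test is not upheld, although 1.44 still exceeds 1. Among trials that pass Section 13.9 first, the readings disagree for observed-case means from 1.50 to 1.63. The section opens by saying that the study hypothesis will be tested, so its conclusion is the result of that test. The only step that depends on it is multiple imputation, which the section makes optional.

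**5. Confidence limit.** In the example in step 3, the upper 95% limit for the signed mean change is -1.3 + 0.501 = -0.80. This is above -1 and agrees with p = 0.160. Section 13.9 defines the signed difference just above the sentence, and Section 13.3 also writes a decrease as a negative number (-2). The upper limit is therefore the right one for the quantity defined.

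**6. The sections side by side.** The synopsis, 13.2, 13.3 and 13.9 share the 1-point margin. Sections 13.3 and 13.9 share the test, the side and the alpha. No section adopts a rule on the observed mean. The synopsis wording, that the change must show a decrease beyond 1 point, is a necessary condition: any result that passes the test also meets it.

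**The case for a change.** The best case for a change is that a success criterion should be written and not inferred. The linking sentence is indeed absent. On the literal reading the gap is large: observed decreases from 1.0 to about 1.5 would count as success after the planned test had failed. The repair would take a few sentences, and it is better made before results are known, because a later clarification could look driven by the outcome.

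The textual point stands: the synopsis omits the test and Section 13.9 does not use the word success. The arithmetic stands too, but it describes a rule that no statistical section contains. To claim success at 1.3 points with p = 0.160, the sponsor would have to disregard the only prespecified primary analysis. A synopsis is expected to compress, and this one keeps the right margin under the matching endpoint label. The limb on Section 13.5 does not stand, since that section itself ties the conclusion to the hypothesis test. The confidence-limit point is one of style: the p-value decides, and the limit is reported in addition.

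**Conclusion.** The concern does not call for a change. The plan has one hypothesis, one margin of 1 point, one one-sided paired t-test and one alpha of 0.05, and its minimum of 36 subjects reproduces on that test. An analyst following it would declare success only on rejecting the Section 13.9 null, and would judge the imputed analysis in Section 13.5 by the same test.

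If the literal reading were adopted, the readings would differ at the planning value in about 10% of trials with 36 subjects, 5% with 45 and 3% with 50; they would differ in about 45% at a true decrease of exactly 1. These figures assume an SD of 2 and roughly normal changes. On the reading that the statistical sections support, the difference is nil. A cross-reference from the synopsis to Section 13.9 would be tidy, but it would change no sample size, analysis or conclusion.
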